5) **ART adherence** will be assessed using the ACTG 4-Day ART Recall Questionnaire based on the 12 month research visit or phone call. Poor adherence will be defined as missing one or more pills in the past 4 days. Participant who died or withdrew before 12 months will be excluded from the analysis. Stratification will be used to adjust for competing risks, if necessary.

Intervention fidelity and completion

An experienced social scientist independent of the conduct unannounced field visit to observe approximately 5% of the intervention sessions of each social worker. The social scientist observed and rated the fidelity of the intervention session using a structured form including the four core elements of DARAJA intervention. A score was provided on a scale of zero to four for each observed intervention session. We will report the average fidelity scores. We will also report the number of intervention participants who completed all 5 prescribed sessions and reasons for participants who did not complete all 5 sessions including died vs. unavailable vs. moved before completing all 5 sessions.

Subgroup analyses

[figure not shown]
For any primary or secondary outcomes that are statistically significant, we will conduct subgroup analyses to see if the effect differs by sex. For time-to-event analyses, stratification and interaction p-values will be used to assess for effect modification. For categorical outcomes, stratification with Cochran–Mantel–Haenszel statistics will be used determine if the benefit/harm of the intervention differed significantly by age group (<> median age), sex or any other variables of particular interest.

Proposed tables and figures

Proposed Table 1: Baseline characteristics among participants in DARAJA clinical trial (with question numbers from the baseline survey)

Variable		Intervention (N = 250)	Control (N = 250)
		n(%)	n(%)
	Age in years (Q105 or Q106)		
sex	Sex (Q104)		
marst	Marital Status (Q108)		
head	Head of household?		
edlev	Education level (Q113)		
Insorc_recat	Occupation		
earn	Income level		
alcohol	Alcohol use (current / ever)		
antiretroviralsp	ART use (new diagnosis)		
healthinsu	Health Insurance		
	Yes		
	No		
bmi	BMI		
sbp	SBP		
cdcount	CD4		
haemoglobin	Hemoglobin		
admin_hosp	Admission Hospital		
depression	Depression (PHQ 9 < 10 vs. >=10)		
covid	COVID time period (pre COVID vs. COVID time period)		

Proposed Figure 1: Flow diagram for screening to enrollment from 20 study sites

Proposed Figure 2: Kaplan-Meier curves for survival by study arms with log rank test (primary outcome)

Proposed Figures 3A/3B: Nelson-Aalen curves for time to linkage and ART initiation in study arms with log rank test (secondary outcomes)

Proposed Table 2: Secondary outcome table for viral suppression, HIV clinic retention, and ART adherence

Secondary Outcome	Intervention (N = ??*)	Control (N = ??*)	p-value (Fisher's exact test)
	n(%)	n(%)	
Viral load suppression (“hvl_status”)			
Suppressed			
Not suppressed			
HIV clinic retention at 12 months (“retention”)			
Retained on ART			
Not retained on ART			
ART Adherence at 12 months (“adherence”)			
100% Adherent			
Not adherent			

* N= 250 minus participants who died / withdrew

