Secondary Aim 2: Gelberg and Andersen Model. The factors in the Gelberg and Andersen Healthcare Utilization Model for Vulnerable Populations will be evaluated using **structural equation modeling** (SEM) to take into account modeling of interactions, nonlinearities, and correlated independent variables. *A priori*, we will create a path analysis of direct and indirect pathways in the Gelberg and Andersen Model domains of predisposing, enabling and need variables. Our model selection will be guided by Information criteria (e.g., AIC/BIC) along with methods for addressing model selection uncertainty provided in Preacher and Merkle (76). We will evaluate the effect of randomization arm upon factors and pathways associated with the primary outcome (survival) as well as secondary outcomes (linkage to HIV clinic). We will also perform **mediation analysis** to determine which factors from the Model act as mediators and moderators of the primary and secondary outcomes, allowing us to explore how and for whom the intervention worked. Short and longer mediation pathways will be tested such as the direct effect of increased self-efficacy on early linkage vs. the effect of increased self-efficacy leading to early linkage leading to survival. Moderation analysis will be conducted to identify (or rule out) potential differential intervention effects for selected subgroups such as whether the intervention is more effective in HIV-infected adults who were ART-naive vs. ART-experienced.

Secondary Aim 3: Acceptability and Barriers/Facilitators of Linkage: All qualitative interviews will be transcribed verbatim, translated in English, and then entered into qualitative software (e.g. Atlas-ti) for coding and analysis. A thematic coding scheme will be created following the main points of the interview guide. To ensure inter-rater reliability of 85%, using Cohen's Kappa (κ) index, [name] and her assistant will code the first five transcripts independently, and then compare their results, and discuss ambiguities and inadequacies in the coding scheme. Refinements to the coding scheme will be made via discussion between [name] and the PI. [name] and her assistant will then code a second set of 5 transcripts, and come together again to compare their results a second time, discuss remaining ambiguities, and achieve consensus in the coding scheme. Based on our previous experience, it is expected that an inter-rater reliability of 75% or

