We will also conduct a secondary “per-protocol” analysis. In this analysis, we will exclude all participants who died before 90 days since these participants could not have completed all 5 sessions according to the protocol. Among participant who survived to 90 days in both arms, we will use proportional hazard cox regression to determine whether intervention participants who completing all 5 sessions experienced a lower hazards of mortality from 90 days to 1 year compared to control participants.

Secondary endpoints

The secondary endpoints considered in this analysis will be **linkage and other steps in the HIV Care Continuum**. Most secondary outcome variables will be determined by medical record extraction from the HIV clinic electronic medical record (except ART adherence). Medical record extraction was performed every 3 months using a standardized CRF ("Follow-up Medical Records Data Extraction Form").

Linkage and ART initiation will be defined as the first visit to the outpatient HIV clinic after enrollment and the time of ART initiation, respectively. Twelve-month retention will be defined as being alive and on ART between 10 and 12 months. HIV RNA levels are retrieved from the EMR. HIV viral suppression will be defined as being alive and on ART with a plasma HIV RNA level <1,000 copies/ μ l according to the World Health Organization definition. Participants who have \geq 1,000 copies/ μ l will be considered unsuppressed. Adherence will be measured with a 4-day recall questionnaire during the 12 month interview.

Time to linkage and ART initiation will be measured in days from the date of randomization to the first HIV clinic (CTC) visit or ART initiation, respectively. For participants without linkage, follow up time will be censored at the date of lost-to-follow up (defined as the date that the research team last had contact with the participant by phone call or face-to-face visit), death, or study end, whichever happens first. Time to linkage and ART initiation will be compared between groups using the log-rank test. We will conduct adjusted analyses using Cox regression. HIV clinic retention, ART adherence and viral suppression will be treated as binary outcomes at 12 months. We will compare these outcomes between study arms using the Fisher exact test. We will conduct adjusted analyses using multivariable adjusted logistic regression. Cochran–Mantel–Haenszel statistics will be used for subgroup analyses.

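### The SAP uses the Cochran-Mantel-Haenszel statistic to judge whether effects on the binary outcomes differ between subgroups, but it tests the pooled effect

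*SAP*

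**What the plan says.** Three outcomes are concerned. Under Secondary endpoints the SAP states that "HIV clinic retention, ART adherence and viral suppression will be treated as binary outcomes at 12 months". They are compared between arms with the Fisher exact test, and for adjustment "We will conduct adjusted analyses using multivariable adjusted logistic regression". The same paragraph ends: "Cochran–Mantel–Haenszel statistics will be used for subgroup analyses".

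The Subgroup analyses section opens with a condition: "For any primary or secondary outcomes that are statistically significant, we will conduct subgroup analyses to see if the effect differs by sex". It then separates the two outcome types. For the first, "For time-to-event analyses, stratification and interaction p-values will be used to assess for effect modification". For the second, "For categorical outcomes, stratification with Cochran–Mantel–Haenszel statistics will be used determine if the benefit/harm of the intervention differed significantly by age group", followed by sex and any other variable of interest.

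The protocol (Data Analysis, Secondary Aim 1) lists CMH beside logistic regression as a method of adjustment for these outcomes. Its only statement on effect modification is under Secondary Aim 2: "Moderation analysis will be conducted to identify (or rule out) potential differential intervention effects for selected subgroups". That belongs to the structural equation work and names no test for retention, suppression or adherence.

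**The concern.** Whether benefit or harm differs significantly between subgroups is a question about effect modification. CMH answers another question: whether arm and outcome are associated after stratifying. A small CMH p-value is what a uniform benefit should produce.

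The order of analyses makes this worse. Subgroups are examined, at least for sex, only after a significant overall result. By then the CMH p-value is almost certain to be small whether or not the effect varies. Read as the SAP says, it would turn a uniform gain in retention, suppression or adherence into a reported difference by sex or age. Conversely, effects in opposite directions can cancel in the pooled statistic and be missed.

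Survival, linkage and ART initiation are not exposed, because interaction p-values are named for time-to-event outcomes.

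**Working it through.** The documents give no figure for these subgroup tests, so there is none to reproduce. The check is a worked example followed by a simulation. Outcome rates and stratum counts are assumptions.

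**Inputs**
- Evaluable numbers: the footnote to SAP Proposed Table 2 sets the denominator, "N= 250 minus participants who died / withdrew". With survival of 90% and 75% from the primary hypothesis and no withdrawals, this is 250 × 0.90 = 225 and 250 × 0.75 = 187.5, taken as 188.
- Two-sided 0.05, as the SAP states for the primary analysis.
- Two strata, about 50:50, as for a median age split. The protocol also expects 50% women (Inclusion of Women and Minorities), while its pilot had 65%.

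**Formulas.** In each stratum, a is the number of intervention successes, n1 and n0 the arm sizes, m the total successes and N = n1 + n0.
- CMH: E = n1·m/N; V = n1·n0·m·(N−m)/[N²(N−1)]; X² = [Σ(a−E)]²/ΣV on 1 df, no continuity correction.
- Interaction (Wald): z = (ln OR₁ − ln OR₂)/√(v₁+v₂), where v is the sum of reciprocals of the four cell counts.

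**Worked example.** Both cases have arm totals 191/225 (85%) vs 141/188 (75%), Fisher p = 0.013.

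| | Stratum 1 | Stratum 2 |
|---|---|---|
| Case A counts | 96/113 vs 71/94 | 95/112 vs 70/94 |
| a − E | 96 − 91.164 = 4.836 | 95 − 89.709 = 5.291 |
| V | 8.038 | 8.187 |
| Odds ratio | 1.83 | 1.92 |
| Case B counts | 107/113 vs 71/94 | 84/112 vs 70/94 |
| a − E | 107 − 97.169 = 9.831 | 84 − 83.728 = 0.272 |
| V | 6.212 | 9.691 |
| Odds ratio (95% CI) | 5.78 (2.24-14.90) | 1.03 (0.55-1.93) |

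- Case A (near-identical effects): X² = 10.127²/16.226 = 6.32, CMH p = 0.012. Interaction z = (0.604 − 0.650)/0.502 = −0.09, p = 0.93. Breslow-Day p = 0.93.
- Case B (effect in one stratum): X² = 10.103²/15.903 = 6.42, CMH p = 0.011. Interaction z = (1.754 − 0.028)/0.581 = 2.97, p = 0.003. Breslow-Day p = 0.002.

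CMH cannot tell the two cases apart; the interaction and homogeneity tests can.

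**Simulation.** 20,000 trials per scenario; 225/188, 225/225 or 250/250 evaluable; strata 50:50 or 65:35; stratum sizes fixed or binomial. The entries are the share of trials with p < 0.05.

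| True effect (intervention vs control) | CMH | Interaction |
|---|---|---|
| Uniform 85% vs 75%, all trials | 72-80% | about 5% |
| Same, given significant Fisher test | 99.7-100% | about 5% |
| One stratum only (95% vs 75%; 75% vs 75%), given significant Fisher test | 97-100% | 91-95% (84-91% if the effect is in the 35% stratum) |
| Opposite (90% vs 75%; 75% vs 90%), 50:50, all trials | 4-5% | 98-99.5% |

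With a continuity correction, the two conditional CMH figures become 96.5-99.8% and 92-100%. A uniform 10-point effect at control rates of 60% and 85% gives CMH 56-97% and interaction 3-5%. With opposite effects the Fisher condition is itself met in only 3-4% of trials at 50:50 (about 20-23% at 65:35). The last row therefore matters mainly if the condition covers only sex, so that an age split is examined regardless.

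**The case against.** The strongest reply is that the sentence is shorthand. It speaks of stratification together with CMH statistics, straight after a sentence that correctly names interaction p-values, so the authors know what such a test is. They may have meant stratum-specific estimates with a homogeneity test alongside. An analyst looking at odds ratios of 1.83 and 1.92 would hardly report a difference.

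That reading is possible and the documents do not exclude it. But it leaves the SAP with no named test for a claim of significant difference. It also fits poorly with the Secondary endpoints section, which moves CMH from the adjusting role it has in the protocol to subgroup analysis.

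Two further points stand in part. The 250/250 scenario requires that nobody dies or withdraws, and 225/188 allows for no withdrawals; neither alters the pattern. A figure under the Subgroup analyses heading could not be read in the text available, so statements about what the SAP omits apply to the readable text. The objection that a Breslow-Day test would serve equally well is fair.

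**Conclusion.** The concern holds. As written, the SAP assigns a test of the pooled effect to a question about differences between strata, and names no suitable test for the three binary outcomes. That conclusion follows from the hypothesis CMH tests and does not depend on the assumed rates; the percentages do.

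The consequence is limited. Only subgroup statements on retention, viral suppression and adherence could be wrong. The primary log-rank test, the Fisher comparisons and the time-to-event subgroup analyses are untouched, and none of the readable proposed tables or figures reports these subgroup results. Minor.

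**What to change.** In the SAP's Subgroup analyses section, replace CMH as the test of effect modification, keep the existing list of subgroup variables, and align the closing sentence of the Secondary endpoints paragraph. Suggested text:

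> For retention, viral suppression and adherence, effect modification by age group (split at the median), sex and any other listed variable will be assessed by the arm-by-subgroup interaction p-value from logistic regression, reported with the estimate and 95% confidence interval in each stratum.

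A Breslow-Day test would also close the gap. The interaction term is suggested because the logistic model is already planned and it matches the time-to-event rule. CMH may stay as a stratum-adjusted overall estimate.

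The cost is one dated SAP change using the same data. The SAP Introduction describes the end line survey as already conducted, so the change should record whether arm-level results had been seen.

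The drawback is limited power. For an effect in one stratum only (80% vs 60%, none in the other), the interaction test rejects in about 58-72% of simulated trials. A non-significant result should be read with the stratum intervals, not as proof of a uniform effect.
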